### **9.3. Causality assessment**

The investigator is required to assess and record the causal relationship. For all AEs, sufficient information should be obtained by the investigator to determine the causality of each AE. For AEs with a causal relationship to Xeljanz, follow-up by the investigator is required until the event and/or its sequelae resolve or stabilize at a level acceptable to the investigator, and Pfizer concurs with that assessment.

An investigator's causality assessment is the determination of whether there exists a reasonable possibility that Xeljanz caused or contributed to an AE. If the investigator's final determination of causality is "unknown" and s/he cannot determine whether Xeljanz caused the event, the safety event must be reported within 24 hours.

If the investigator cannot determine the etiology of the event but s/he determines that Xeljanz did not cause the event, this should be clearly documented on the CRF and the NIS AEM Report Form.

### **9.4. Definition of safety events**

#### **9.4.1. Adverse events**

An AE is any untoward medical occurrence in a patient administered a medicinal product. The event need not necessarily have a causal relationship with the product treatment or usage. Examples of AEs include but are not limited to:

- Abnormal test findings (see below for circumstances in which an abnormal test finding constitutes an AE);
- Clinically significant symptoms and signs;
- Changes in physical examination findings;
- Hypersensitivity;
- Progression/worsening of underlying disease;
- Lack of efficacy;

- Drug abuse;
- Drug dependency.

Additionally, for medicinal products, they may include the signs or symptoms resulting from:

- Drug overdose;
- Drug withdrawal;
- Drug misuse;
- Off-label use;
- Drug interactions;
- Extravasation;
- Exposure during pregnancy;
- Exposure during breast feeding;
- Medication error;
- Occupational exposure.

#### Abnormal test findings

The criteria for determining whether an abnormal objective test finding should be reported as an AE are as follows:

- Test result is associated with accompanying symptoms, and/or
- Test result requires additional diagnostic testing or medical/surgical intervention, and/or
- Test result leads to a change in study dosing or discontinuation from the study, significant additional concomitant drug treatment, or other therapy, and/or
- Test result is considered to be an AE by the investigator or sponsor.

Merely repeating an abnormal test, in the absence of any of the above conditions, does not constitute an AE. Any abnormal test result that is determined to be an error does not require reporting as an AE.

#### **9.4.2. Serious adverse events**

A SAE is any untoward medical occurrence in a patient administered a medicinal or nutritional product (including pediatric formulas) at any dose that:

- Results in death;
- Is life-threatening;
- Requires inpatient hospitalization or prolongation of hospitalization (see below for circumstances that do not constitute AEs);
- Results in persistent or significant disability/incapacity (substantial disruption of the ability to conduct normal life functions);
- Results in congenital anomaly/birth defect.

Medical and scientific judgment is exercised in determining whether an event is an important medical event. An important medical event may not be immediately life-threatening and/or result in death or hospitalization. However, if it is determined that the event may jeopardize the patient or may require intervention to prevent one of the other outcomes listed in the definition above, the important medical event should be reported as serious.

Examples of such events are intensive treatment in an emergency room or at home for allergic bronchospasm; blood dyscrasias or convulsions that do not result in hospitalization; or development of drug dependency or drug abuse.

In this study, the onset of disease includes but is not limited to the following, which should be considered as medically important SAEs of special interest: serious infection, tuberculosis, cancer, or lymphocyte proliferative disorders. These events will be monitored, analyzed, and reported.

Additionally, any suspected transmission via a Pfizer product of an infectious agent, pathogenic or non-pathogenic, is considered serious. The event may be suspected from clinical symptoms or laboratory findings indicating an infection in a patient exposed to a Pfizer product. The terms “suspected transmission” and “transmission” are considered synonymous. These cases are considered unexpected and handled as serious expedited cases by pharmacovigilance personnel. Such cases are also considered for reporting as product defects, if appropriate.

#### Hospitalization

Hospitalization is defined as any initial admission (even if less than 24 hours) to a hospital or equivalent healthcare facility or any prolongation to an existing admission. Admission also includes transfer within the hospital to an acute/intensive care unit (eg, from the psychiatric wing to a medical floor, medical floor to a coronary care unit, neurological floor to a tuberculosis unit). An emergency room visit does not necessarily constitute a hospitalization;

however, an event leading to an emergency room visit should be assessed for medical importance.

Hospitalization in the absence of a medical AE is not in itself an AE and is not reportable. For example, the following reports of hospitalization without a medical AE are not to be reported.

- Social admission (eg, patient has no place to sleep);
- Administrative admission (eg, for yearly exam);
- Optional admission not associated with a precipitating medical AE (eg, for elective cosmetic surgery);
- Hospitalization for observation without a medical AE;
- Admission for treatment of a pre-existing condition not associated with the development of a new AE or with a worsening of the pre-existing condition (eg, for work-up of persistent pre-treatment lab abnormality);
- Protocol-specified admission during clinical study (eg, for a procedure required by the study protocol).

#### **9.4.3. Scenarios necessitating reporting to Pfizer Safety within 24 hours**

Scenarios involving exposure during pregnancy, exposure during breastfeeding, medication error, overdose, misuse, extravasation, lack of efficacy, and occupational exposure are described below.

##### Exposure during pregnancy

An exposure during pregnancy (EDP) occurs if:

1. A female becomes, or is found to be, pregnant either while receiving or having been exposed to (eg, environmental) Xeljanz or the female becomes, or is found to be, pregnant after discontinuing and/or being exposed to Xeljanz (maternal exposure).

An example of environmental exposure would be a case involving direct contact with a Pfizer product in a pregnant woman (eg, a nurse reports that she is pregnant and has been exposed to chemotherapeutic products).

2. A male has been exposed, either due to treatment or environmental exposure to Xeljanz prior to or around the time of conception and/or is exposed during the partner pregnancy (paternal exposure).

As a general rule, prospective and retrospective exposure during pregnancy reports from any source are reportable, irrespective of the presence of an associated AE and the procedures for SAE reporting should be followed.

If a study participant or study participant's partner becomes, or is found to be, pregnant during the study participant's treatment with Xeljanz, this information must be submitted to Pfizer, irrespective of whether an AE has occurred using the NIS AEM Report Form and the EDP Supplemental Form.

In addition, the information regarding environmental exposure to Xeljanz in a pregnant woman (eg, a patient reports that she is pregnant and has been exposed to a cytotoxic product by inhalation or spillage) must be submitted using the NIS AEM Report Form and the EDP supplemental form. This must be done irrespective of whether an AE has occurred.

Information submitted should include the anticipated date of delivery (see below for information related to termination of pregnancy).

Follow-up is conducted to obtain general information on the pregnancy; in addition, follow-up is conducted to obtain information on EDP outcome for all EDP reports with pregnancy outcome unknown. A pregnancy is followed until completion or until pregnancy termination (eg, induced abortion) and Pfizer is notified of the outcome. This information is provided as a follow up to the initial EDP report. In the case of a live birth, the structural integrity of the neonate can be assessed at the time of birth. In the event of a termination, the reason(s) for termination should be specified and, if clinically possible, the structural integrity of the terminated fetus should be assessed by gross visual inspection (unless pre-procedure test findings are conclusive for a congenital anomaly and the findings are reported).

If the outcome of the pregnancy meets the criteria for an SAE (eg, ectopic pregnancy, spontaneous abortion, intrauterine fetal demise, neonatal death, or congenital anomaly [in a live born, a terminated fetus, an intrauterine fetal demise, or a neonatal death]), the procedures for reporting SAEs should be followed.

Additional information about pregnancy outcomes that are reported as SAEs includes:

- Spontaneous abortion includes miscarriage and missed abortion;
- Neonatal deaths that occur within 1 month of birth should be reported, without regard to causality, as SAEs. In addition, infant deaths after 1 month should be reported as SAEs when the investigator assesses the infant death as related or possibly related to exposure to the investigational product

Additional information regarding the exposure during pregnancy may be requested. Further follow-up of birth outcomes will be handled on a case-by-case basis (eg, follow-up on preterm infants to identify developmental delays).

In the case of paternal exposure, the study participant will be provided with the Pregnant Partner Release of Information Form to deliver to his partner. It must be documented that the study participant was given this letter to provide to his partner.

#### Exposure during breastfeeding

Scenarios of exposure during breastfeeding must be reported, irrespective of the presence of an associated AE. An exposure during breastfeeding report is not created when a Pfizer drug specifically approved for use in breastfeeding women (eg, vitamins) is administered in accord with authorized use. However, if the infant experiences an AE associated with such a drug's administration, the AE is reported together with the exposure during breastfeeding.

#### Medication error

A medication error is any unintentional error in the prescribing, dispensing or administration of a medicinal product that may cause or lead to inappropriate medication use or patient harm while in the control of the health care professional, patient, or consumer. Such events may be related to professional practice, health care products, procedures, and systems including: prescribing; order communication; product labeling, packaging, and nomenclature; compounding; dispensing; distribution; administration; education; monitoring; and use.

Medication errors include:

- Near misses, involving or not involving a patient directly (eg, inadvertent/erroneous administration, which is the accidental use of a product outside of labeling or prescription on the part of the healthcare provider or the patient/consumer);
- Confusion with regard to invented name (eg, trade name, brand name).

The investigator must submit the following medication errors to Pfizer, irrespective of the presence of an associated AE/SAE:

- Medication errors involving patient exposure to the product, whether or not the medication error is accompanied by an AE.
- Medication errors that do not involve a patient directly (eg, potential medication errors or near misses). When a medication error does not involve patient exposure to the product the following minimum criteria constitute a medication error report:
  - An identifiable reporter;
  - A suspect product;
  - The event medication error.

#### Overdose, Misuse, Extravasation

Reports of overdose, misuse, and extravasation associated with the use of a Pfizer product are reported to Pfizer by the investigator, irrespective of the presence of an associated AE/SAE.

#### Lack of Efficacy

Reports of lack of efficacy to a Pfizer product are reported to Pfizer by the investigator, irrespective of the presence of an associated AE/SAE or the indication for use of the Pfizer product.

#### Occupational Exposure

[figure not shown]
Reports of occupational exposure to a Pfizer product are reported to Pfizer by the investigator, irrespective of the presence of an associated AE/SAE.

#### **9.5. Single reference safety document**

The local product document will serve as the SRSD during the course of the study, which will be used by Pfizer safety to assess any safety events reported to Pfizer Safety by the investigator during the course of this study.

The SRSD should be used by the investigator for prescribing purposes and guidance.

CCI

### **COMMUNICATION OF ISSUES**

In the event of any prohibition or restriction imposed (eg, clinical hold) by an applicable Competent Authority in any area of the world, or if the investigator is aware of any new information which might influence the evaluation of the benefits and risks of a Pfizer product, Pfizer should be informed immediately.

In addition, the investigator will inform Pfizer immediately of any urgent safety measures taken by the investigator to protect the study patients against any immediate hazard, and of any serious breaches of this NIS protocol that the investigator becomes aware of.

## **12. LIST OF TABLES**

Table 1 Recommended Laboratory Test

Table 2 American College of Rheumatology Preliminary Definition of Improvement in Rheumatoid Arthritis

## **13. LIST OF FIGURES**

Figure 1 DAS28-based EULAR response criteria

## **ANNEX 1. LIST OF STAND ALONE DOCUMENTS**

None.

## **ANNEX 2. ADDITIONAL INFORMATION**

Not applicable.

Statistical Analysis Plan

1. Rationale and Background

Xeljanz® (tofacitinib) is a potent, oral janus kinase inhibitor. Xeljanz® was approved by the Ministry of Food and Drug Safety (MFDS) on 02 April 2014 for the treatment of adult patients with moderately to severely active rheumatoid arthritis (RA) who have had an inadequate response or intolerance to methotrexate. It may be used as monotherapy or in combination with methotrexate or other non biologic disease-modifying anti-rheumatic drugs (DMARDs).

In addition, MFDS approved new indications for the treatment of adult patients with active psoriatic arthritis (PsA) who have had an inadequate response or intolerance to previous antirheumatic drugs (DMARDs) on 20 Sep 2018. It may be used in combination with methotrexate or other nonbiologic disease-modifying anti-rheumatic drugs (DMARDs). The efficacy of Xeljanz as a monotherapy has not been studied in psoriatic arthritis.

Background information on Xeljanz® can be obtained from the current version of the local product document (ie, local labelling), which is the single reference safety document (SRSD) for information relating to Xeljanz® in this study.

2. Study Objective(s) and Others

2.1. Study Objective

The objective of this study is to identify any problems and questions with respect to the safety and efficacy of Xeljanz® during the post-marketing period as required by the regulation of MFDS.

2.2. Study Design

2.2.1. General Study Design

This is an open-label, non-comparative, non-interventional, prospective, and multi-center study conducted in Korean health care centers by accredited physicians (ie, investigators). The study population will be adult patients with moderately to severely active RA who have had an inadequate response or intolerance to methotrexate. Xeljanz® will be administered according to the "Dosage and Administration" of the approved labeling. There is no visit or activity mandated by this study. The investigator will collect patient data and record the information on each patient's case report form (CRF).

Statistical Analysis Plan

CCI

Also, investigators collect data on the Xeljanz retrospectively from the subjects who have been administered the Xeljanz according to the local product documents but not participated in this study for 2 years after completion of re-examination.

Safety is the primary interest of this study, which will be assessed based on adverse events (AEs) that occur during the 6 months from the first dose of Xeljanz®. The efficacy endpoints will be the modified Disease Activity Score using 28 joint counts (DAS28) change from baseline, European League Against Rheumatism (EULAR) response, and American College of Rheumatology 20% improvement criteria (ACR20) response after treatment.

2.2.2. Duration of the Study

CCI
CCI

The re-examination period is from 02 April

2014 to 01 April 2020, and the final study report should therefore be submitted by 01 July 2020. Additional safety and effectiveness result report from prospective and retrospective studies for additional 2 years would be submitted as part of RMP in accordance with local regulations.

2.3. Study Population

2.3.1. Inclusion Criteria

All patients will have received at least 1 dose of Xeljanz® for the treatment of the following indication as per local labelling. Patients must meet all of the following inclusion criteria to be eligible for inclusion in the study.

- Moderately to severely active RA in adult patients who have had an inadequate response or intolerance to methotrexate.
- Active psoriatic arthritis (PsA) in adult patients who have had an inadequate response or intolerance to previous antirheumatic drugs (DMARDs).
- Evidence of a personally signed and dated informed consent document indicating that the patient (or a legally acceptable representative) has been informed of all pertinent aspects of the study (In case of subjects to be collected data retrospectively, whether or not to obtain the informed consent document depends on the decision by the institutional review board

Statistical Analysis Plan

(IRB)/independent ethics committee (IEC).).

2.3.2. Exclusion Criteria

Patients meeting any of the following criteria as per the local labeling will not be included in the study.

- 1) Patients with a history of hypersensitivity to any ingredients of this product.
- 2) Patients with serious infection (sepsis, etc.) or active infection including localized infection.
- 3) Patients with active tuberculosis.
- 4) Patients with severe hepatic function disorder.
- 5) Patients with an absolute neutrophil count (ANC) <1,000 cells/mm³*
- 6) Patients with a lymphocyte count <500 cells/mm³.
- 7) Patients with a hemoglobin level <9 g/dL*.
- 8) Pregnant or possibly pregnant women.
- 9) Because of lactose contained in this drug, it should not be administered to patients with hereditary problems of galactose intolerance, Lapp lactase deficiency or glucose-galactose malabsorption.

* For patients who develop the laboratory abnormalities as follows, it should be discontinued Xeljanz® dosing according to the 'warning and precautions' in the local labelling.
- Patients with an ANC <500 cells/mm³.
- Patients with a hemoglobin level <8 g/dL.

3. Analysis Populations

3.1. Safety Analysis Set

Safety analysis set will be included all patients who have received at least 1 dose of Xeljanz® according to local product document and have been assessed for safety information including AEs by investigator.

Statistical Analysis Plan

The following cases will be excluded from the safety analysis set.

- Patients who have been enrolled and completed before contracting with health care center.
- Patients who have not been administered for Xeljanz®.
- Patients who have not met the inclusion/exclusion criterion.
- Patients who have experienced off-label use against Xeljanz® local product document.

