### **7.7.1. Safety analysis**

[figure not shown]
The primary interest of this study is the incidence of AEs investigated during the re-examination period. Incidence of each AE will be presented with 95% confidence interval. Serious, related, and/or unexpected AEs will be summarized separately.

To identify the factors that affect safety, subgroup analysis for various factors will be performed, including the classification of AEs by body system, and comparison of incidence of AEs by sex, age, presence of concurrent diseases, presence of concomitant medications, baseline disease activity, etc.

In case the drug was administered to special populations such as children, elderly people, or patients with renal or hepatic disorders during the study, subgroup analysis will also be performed for each of those populations.

Unexpected AEs/ADRs will be classified by medical review with reference to the local product document. Events already included in the “Precautions for use” section of the local product document will be classified as “expected”. All other events that are not included in the “Precautions for use” section of the local product document will be classified as “unexpected”. An unexpected AE includes any events that may be symptomatically and patho-physiologically related to an event listed in the labeling, but differs from the labeled event because of greater severity or specificity.

In the case of an adverse event with important potential risks and important identified risks in relation to the safety specification under the risk management plan, or if missing information patient group is recruited, actions according to the label will be taken, and the safety information is presented separately.

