3.5. Off-label Evaluation Patients

Off-label evaluation patients will be included patients who have experienced off-label use against Xeljanz® local product document during the study.

4. Study Endpoints

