6.4. Safety Analyses

Safety analyses will be performed based on data of safety analysis set. All adverse events in CRF will be classified by System Organ Class (SOC) and Preferred Term (PT) according to the latest version of MedDRA.

- 1) All adverse events investigated after administration of Xeljanz® during the study will be summarized by frequency and percent (n, percentage) by categorizing as follows. Also, it will be presented in n, incidence rate, 95% confidence interval of incidence rate and number of events for each SOC and PT.
 - Frequency analysis of adverse events/adverse drug reactions
 - Frequency analysis of serious adverse events/serious adverse drug reactions
 - Frequency analysis of serious unexpected adverse events/serious unexpected adverse drug reactions
 - Frequency analysis of unexpected adverse events/unexpected adverse drug reactions
 - Frequency analysis of adverse events of special interest/adverse drug reactions of special interest
 - Occurrence status of adverse events/adverse drug reactions by its seriousness
 - Results in death
 - Is life-threatening
 - Requires inpatient hospitalization or prolongation of hospitalization
 - Results in persistent or significant disability/incapacity
 - Results in congenital anomaly/birth defect
 - Important medical event: if it is determined that the event may jeopardize the patient or may require intervention to prevent one of the other outcomes listed in the definition above
 - Occurrence status of adverse events/adverse drug reactions by its severity
 - Mild
 - Moderate
 - Severe
 - Occurrence status of adverse events/adverse drug reactions by its causality assessment
 - Related to this medicinal product: ① Certain

Statistical Analysis Plan

- ② Probable/likely
- ③ Possible
- ⑤ Conditional/unclassified
- ⑥ Unassessable/unclassifiable

- Not related to this medicinal product: ④ Unlikely
- Occurrence status of adverse events/adverse drug reactions by its action taken
 - Permanently discontinued
 - Temporarily discontinued or delayed
 - Dose reduced
 - Dose increased
 - No change
 - Not applicable
- Occurrence status of adverse events/adverse drug reactions by its outcome
 - Recovered
 - Recovered with sequelae
 - Recovering
 - Not recovered
 - Unknown

2) Occurrence status of adverse events by demography and baseline characteristics

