Occurrence status of adverse events will be presented in frequency and percentage and incidence rate with 95% confidence interval based on categorical variables of demography and baseline characteristics of the patients. To identify statistically significant difference in occurrence of adverse events by demography and baseline characteristics, Chi-square test or Fisher's exact test will be performed.

3) Occurrence status of adverse events by concomitant treatment

Occurrence of adverse events will be presented in frequency and percentage and incidence rate of adverse events with 95% confidence interval by concomitant treatment status. To identify statistically significant difference in occurrence of adverse events by concomitant treatment status, Chi-square test or Fisher's exact test will be performed.

4) Analysis of factors that affect the safety

In the re-examination report, logistic regression analysis of multivariate analysis will be performed and presented an odds ratio with 95% confidence interval to identify the factors that affect occurrence of adverse events in demography and baseline characteristics, or concomitant treatment status, etc.

5) Distribution for special patient populations (elderly (age over 65 years old), renal disorder, hepatic disorder) will be presented. Also, adverse events and adverse drug reactions collected

Statistical Analysis Plan

by these groups will be presented in incidence rate and number events of it for each SOC and PT.

[figure not shown]
- For children and pregnant women, it will be performed in off-label patient analysis because administration of children (age less than 19 years old) and pregnant women is contraindicated according to the local product document.

6) Distribution for off-label evaluation patients will be presented. Also, adverse events and adverse drug reactions collected by these groups will be presented in incidence rate and number events of it for each SOC and PT.

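### SAP 3.1 removes a patient from the safety set for off-label use at any time, even after an on-label start, and the off-label output in SAP 6.4 gives those patients no serious-AE summary (minor)

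*SAP*

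**What the plan says.** SAP 3.1 builds the safety set from patients with at least one on-label dose and a safety assessment. It then lists four exclusions, the last being "Patients who have experienced off-label use against Xeljanz® local product document". SAP 3.5 collects the same people into a separate group, "patients who have experienced off-label use against Xeljanz® local product document during the study".

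SAP 6.4 opens with "Safety analyses will be performed based on data of safety analysis set". Item 1 lists the tables on that set, including "Frequency analysis of serious adverse events/serious adverse drug reactions" and a breakdown by seriousness criterion. Item 5 adds: "For children and pregnant women, it will be performed in off-label patient analysis", because use in both groups is contraindicated. Item 6 covers the separated group: "Distribution for off-label evaluation patients will be presented. Also, adverse events and adverse drug reactions collected by these groups will be presented", as rates and event counts by system organ class (SOC) and preferred term (PT).

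Protocol 7.3.1 assesses safety in every patient with at least one on-label dose. Protocol 7.7.1 states: "Serious, related, and/or unexpected AEs will be summarized separately".

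**The concern.** Safety is the primary interest of the study. An analysis set defined partly by what happens after first dose can lose patients for reasons linked to how treatment went. Here the whole patient is removed, not only the off-label portion of follow-up, so AEs that occurred during proper use are lost from the main tables as well.

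The output that takes over has less content than the one she or he left. A serious AE in an off-label patient is counted by PT, but nothing planned for that group says that it was serious. At stake are individual rows in the serious-AE tables, where one case can be the whole finding. The overall AE rate is hardly affected.

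**Working it through.** The plan gives no figure to reproduce, and the study-size section is redacted. The main check follows one patient through the text.

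1. **Entry.** The patient takes a first dose on label and is assessed for safety. The inclusion clause of SAP 3.1 and Protocol 7.3.1 both admit the patient.
2. **Change of status.** Use later departs from the label. The documents do not reproduce the label, so the triggers cannot be listed in full. One candidate is a patient kept on drug after the absolute neutrophil count falls below 500 cells/mm³, where Protocol 7.3.1.2 says that the label requires stopping.
3. **Removal.** The fourth bullet of SAP 3.1 carries no time limit, and SAP 3.5 refers to the study as a whole. The patient moves to the off-label group with all AEs, including those from before the change. Protocol 7.3.1 contains nothing that would remove the patient.
4. **Tables lost.** The item 1 tables of SAP 6.4 run on the safety set. The patient's serious AEs are therefore absent from the serious-AE table, the serious-unexpected table and the seriousness breakdown.
5. **Tables gained.** Item 6 gives rates and counts by SOC and PT. It mentions neither seriousness nor a confidence interval.
6. **Result.** For a serious AE in this group, the output planned in the SAP does not deliver the separate summary that Protocol 7.7.1 promises. This holds for any patient classed as off-label, whenever the off-label use began.

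**Size, overall incidence.** Let N be all patients with an on-label first dose, k the number later removed, and p the AE proportion among the N − k who remain. If all k had an AE, the shift is [p(N − k) + k]/N − p = k(1 − p)/N. If none had, it is −kp/N. In absolute value it never exceeds k/N. N and k are assumptions:

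- k = 1: 1/500 = 0.20 percentage points; 1/3,000 = 0.03.
- k = 5: 5/500 = 1.00 percentage points; 5/3,000 = 0.17.

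**Size, a rare-event row.** Suppose that the removed patient had the only event of its PT, so the row reads 0 instead of 1. SAP 6.4 names no interval method, so I assume the exact two-sided 95% interval. The upper limit for 0 of N is 1 − 0.025^(1/N). For 1 of N it solves (1 − p)^N + Np(1 − p)^(N−1) = 0.025, with p now the limit sought.

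| Assumed N | Upper limit, 0 events | Upper limit, 1 event |
|---|---|---|
| 500 | 0.74% | 1.11% |
| 1,000 | 0.37% | 0.56% |
| 3,000 | 0.12% | 0.19% |

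The ratio is about 1.5 throughout (for example 1.109/0.735 = 1.51). That is a property of 0 against 1 event at these sizes, not evidence about this study. Using N − 1 as the denominator for the zero row leaves the two-decimal figures unchanged.

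**The case against.** The strongest reply is that separating off-label patients is deliberate. Protocol 7.3.1 ties safety assessment to labelled use, and Protocol 7.9 says that regulation determines the protocol. The separation is also open: Protocol 7.7 requires counts of cases enrolled, retrieved and analysed, and item 6 of SAP 6.4 shows who the off-label patients are and which AEs they had. Serious AEs are recorded on the CRF and reported to the sponsor's safety unit within 24 hours (Protocol 9.1). All of this stands, and it keeps the point minor. It does not supply the missing serious-AE summary, because reporting single cases is a different task from the summary promised in Protocol 7.7.1.

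The last paragraph of Protocol 7.7.1 also provides for separate presentation of risk-management-plan risks and missing-information groups. Some off-label patients may be covered that way. The risk management plan is not available, so this cannot be settled.

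A reader might infer more about pregnancy than the text allows: that a woman who conceives on treatment must leave the safety set, because pregnancy at entry is already barred ("Pregnant or possibly pregnant women") and the off-label rule must therefore be aimed at later conception. That does not follow. Item 5 pairs pregnant women with children, who already fail the adult inclusion criteria, so the off-label group is evidently meant to hold entry violators too. Protocol 9.4.1 lists exposure during pregnancy separately from off-label use, and Protocol 9.4.3 gives conception on drug its own category. SAP 3.3 speaks of dosing during the study without implying onset after baseline. Conception on treatment is a possible example only.

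Nor do the documents support saying that such events disappear. A spontaneous abortion shown by PT in item 6 is recognisable as serious, since Protocol 9.4.3 names it among pregnancy outcomes that qualify.

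**Conclusion.** The point holds as a minor one. Two things are established from the text: the off-label exclusion has no time anchor and removes whole patients whom Protocol 7.3.1 would keep, and the item 6 output omits the serious-AE summary that Protocol 7.7.1 requires. The second does not depend on how the pregnancy wording is read.

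The number of patients affected is not given and is probably very small; with none, the effect is zero. With one to five, and N assumed between 500 and 3,000, overall AE incidence moves by at most 0.03 to 1.00 percentage points. A single rare-event row could read 0 instead of 1, which under the exact interval is a difference of 0.06 to 0.37 points in the upper limit (0.186 − 0.123 and 1.109 − 0.735). Calling that lower limit wrong presumes that events after off-label use began belong in the main rate, which the sponsor may reasonably dispute. For events before the change in use, the case for keeping them is stronger.

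**What to change.** 1. In SAP 6.4 item 6, apply the item 1 serious-AE tables and seriousness breakdown to the off-label patients. This closes the gap with Protocol 7.7.1 whatever is decided below.
2. In SAP 3.1, choose one rule. Either judge off-label status at first dose, keep patients who started on label, and flag later off-label or pregnancy exposure. Or, if the regulator requires separation, keep the present set and add a serious-AE table for all treated patients.
3. In SAP 3.5, state whether conception on treatment counts as off-label use, so that two programmers would build the same set.

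The cost is SAP wording and a rerun of existing tables. Protocol 7.3.1.1 already has seriousness recorded for each AE, so no new data or visits are needed. The drawback is one extra table with a different denominator, which needs a footnote.
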